The target sample size is 3400 patients with neuropathic pain in total, including 3000 patients with peripheral neuropathic pain (1000 patients with postherpetic neuralgia, if possible, and 2000 patients with peripheral neuropathic pain of the types other than postherpetic neuralgia), and 400 patients with central neuropathic pain (300 patients with post-stroke pain, if possible, and other patients with pain following traumatic spinal cord injury and pain due to Parkinson's disease). For peripheral neuropathic pain, approximately 100 each of patients should be accumulated, if possible, for trigeminal neuralgia, peripheral entrapment neuropathy, iatrogenic neuropathy, neuropathy due to tumor-induced nerve compression or infiltration, posttraumatic pain, and chronic cauda equina syndrome.

The target sample size of 3400 patients with neuropathic pain is expected to have a 97% probability to detect adverse reactions occurring at the incidence of 0.1% or higher in at least 1 patient. Of the adverse reactions included in the major investigation items, vision-related events are anticipated to develop at the lowest incidence during the survey. In

clinical studies of Lyrica conducted in Japan and overseas, the lower bound of the 95% confidence interval for the incidence of this adverse reaction was 6.70% (incidence 7.40%, 380/5134 patients). If this adverse reaction develops at the same incidence as in these clinical studies, this reaction is expected to occur in 227 or more of 3400 patients. Since the safety and efficacy of Lyrica should be evaluated in patients with each type of neuropathic pain, enrollment of the following number of patients will be ensured; approximately 100 patients each, if possible, for trigeminal neuralgia, peripheral entrapment neuropathy, iatrogenic neuropathy, neuropathy due to tumor-induced nerve compression or infiltration, posttraumatic pain, and chronic cauda equina syndrome, approximately 300 patients for post-stroke pain, and a certain number of patients for pain following traumatic spinal cord injury and pain due to Parkinson's disease.

This sample size will also allow for adequate evaluation of the characteristics of other adverse reactions included in the major investigation items. The characteristics to be evaluated include time of onset and duration of adverse reactions, and these were also investigated in the clinical studies.

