4.1. Statistical hypothesis

Because this survey is not a confirmatory investigation, the testing should be considered as exploratory in nature. Unless otherwise specified, the 2-sided testing is performed with a significance level of 5%.

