5.4. Subgroups

Subgroup analyses of safety will be performed for the following patient demographics and other factors.

- Hepatic impairment
- Renal impairment
- Children (<15 years), adults (≥ 15 to < 65 years), elderly (≥ 65 years)
- Age [< 65 years, ≥ 65 to < 70 years, ≥ 70 to < 75 years, ≥ 75 to < 80 years, ≥ 80 to < 85 years, ≥ 85 years]
- Sex [male, female]
- Inpatient/outpatient status at the initial prescription [inpatient, outpatient]
- Body weight at the start of treatment (by sex) [< 40 kg, ≥ 40 to < 50 kg, ≥ 50 to < 60 kg, ≥ 60 kg]
- Name of target disease (i.e., diagnosis of neuropathic pain) [by disease name]
- Hemodialysis [no, yes]
- Creatinine clearance [< 15 mL/min, ≥ 15 to < 30 mL/min, ≥ 30 to < 60 mL/min, ≥ 60 mL/min]
- Past medical history [no, yes]
- Complications [no, yes]
- Prior medications [no, yes]
- Concomitant medications [no, yes]
- Non-medication therapies [no, yes]
- Timing of drug administration (at the start of treatment) [before meal, after meal, other]
- Daily dose (at the start of treatment) [≤ 25 mg, > 25 to ≤ 75 mg, > 75 to ≤ 150 mg, > 150 to ≤ 300 mg, > 300 to ≤ 600 mg, > 600 mg]
- Daily dose (maximum) [≤ 25 mg, > 25 to ≤ 75 mg, > 75 to ≤ 150 mg, > 150 to ≤ 300 mg, > 300 to ≤ 600 mg, > 600 mg]
- Pregnant and parturient women (pregnant)

Subgroup analyses of efficacy will be performed for the following patient demographics and other factors.

- Hepatic impairment
- Renal impairment
- Children (<15 years), adults (≥ 15 to < 65 years), elderly (≥ 65 years)
- Age [< 65 years, ≥ 65 to < 70 years, ≥ 70 to < 75 years, ≥ 75 to < 80 years, ≥ 80 to < 85 years, ≥ 85 years]
- Sex [male, female]

- Inpatient/outpatient status at the initial prescription [inpatient, outpatient]
- Body weight at the start of treatment (by sex) [<40 kg, ≥ 40 to <50 kg, ≥ 50 to <60 kg, ≥ 60 kg]
- Name of target disease (i.e., diagnosis of neuropathic pain) [by disease name]
- Hemodialysis [no, yes]
- Creatinine clearance [<15 mL/min, ≥ 15 to <30 mL/min, ≥ 30 to <60 mL/min, ≥ 60 mL/min]
- Past medical history [no, yes]
- Complications [no, yes]
- Prior medications [no, yes]
- Concomitant medications [no, yes]
- Timing of drug administration (at the start of treatment) [before meal, after meal, other]
- Daily dose (at the start of treatment) [≤ 25 mg, >25 to ≤ 75 mg, >75 to ≤ 150 mg, >150 to ≤ 300 mg, >300 to ≤ 600 mg, >600 mg]
- Daily dose (maximum) [≤ 25 mg, >25 to ≤ 75 mg, >75 to ≤ 150 mg, >150 to ≤ 300 mg, >300 to ≤ 600 mg, >600 mg]

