8.1.3. Analysis of binary data

Frequency and its proportion will be calculated. If the confidence interval of proportion is calculated, a 2-sided 95% confidence interval (exact method) will be calculated.

If the proportion is compared between subgroups, Fisher’s exact test and Cochran-Armitage test (exact method) will be performed for the relationships with nominal scale data and ordinal scale data, respectively, and the risk ratio and risk difference with their 95% confidence intervals will be calculated.

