8.2.3.4. Subgroup analysis

Number and proportion of patients with at least one adverse reaction will be tabulated by factor specified in Section 5.4. Tests specified in Section 8.1.3 will be performed to evaluate the relationship between patient demographics, etc. and development of adverse reactions. Furthermore, risk ratio and risk difference for the incidence of adverse reactions and their 95% confidence intervals will be calculated between subgroups.

In addition, number and proportion of patients with adverse reactions in each subgroup will be tabulated by SOC and PT for factors showing a significant difference by testing to evaluate the relationship between patient demographics, etc. and development of adverse reactions. Moreover, patient demographics, etc. (including breakdown of past medical history and complications, prior and concomitant medications) will be tabulated in each subgroup and number and proportion of patients with serious adverse reactions will be tabulated by SOC and PT in each subgroup as necessary.

Laboratory parameters will be tabulated as specified in Section 8.2.3.3 in patients whose target disease is painful diabetic neuropathy.

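### Several safety factors, hemodialysis among them, get a SOC/PT breakdown only if the factor is significant on any adverse reaction, so a specific reaction concentrated in a small group is likely to go unshown by that factor

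*SAP*

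**What the plan says.** SAP 8.2.3.4 opens with the lumped outcome: "Number and proportion of patients with at least one adverse reaction will be tabulated by factor specified in Section 5.4". Each factor is tested by the methods of SAP 8.1.3, that is, Fisher's "exact test and Cochran-Armitage test (exact method) will be performed for the relationships with nominal scale data and ordinal scale data" respectively. SAP 4.1 says that "the 2-sided testing is performed with a significance level of 5" per cent, and also that "the testing should be considered as exploratory in nature"; SAP 4.2 gives no decision rule.

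The next paragraph of 8.2.3.4 makes the detailed output depend on those tests. The number and proportion with adverse reactions in each subgroup "will be tabulated by SOC and PT for factors showing a significant difference by testing". Serious reactions by SOC and PT in each subgroup follow as necessary. Risk ratios and risk differences with 95% intervals are calculated without a significance condition, but for the any-reaction incidence.

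Section 5.4 lists 19 safety factors, including "Hemodialysis [no, yes". Tables that carry no significance condition are:

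- elderly, pediatric, renally impaired and hepatically impaired patients, all and serious reactions by SOC and PT (8.2.3.1);
- two groups defined by creatinine clearance and initial dose, by SOC and PT (8.2.3.1);
- drug classes of prior and concomitant medications, numbers by PT within target diseases of about 100 patients or more (8.2.3.1);
- target disease and initial dose group, by SOC and PT (8.2.3.5);
- the dizziness, somnolence, loss of consciousness, syncope and accidental injury item by every 5.4 factor, though not stated to be by PT (8.2.3.1).

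**The concern.** SAP 2.2 sets out to find unknown adverse reactions and factors that affect safety. A test on any adverse reaction is a poor screen for that. A reaction that is rare overall hardly moves the lumped rate, and in a small group even a sizeable shift is seldom significant.

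The factors with no unconditional SOC/PT table are hemodialysis, clearance below 15 and 15 to below 30 mL/min as separate bands, body weight, sex, inpatient status, past history, complications, non-medication therapy, timing of administration and maximum dose. For them, the p-value on the lumped outcome decides whether the reaction-level data are laid out at all.

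Two of the three major investigation items are affected. Protocol 6.9 promises analysis by background variables for edema, the dizziness group and vision. The SAP writes an unconditional table over all 5.4 factors only for the dizziness group. Edema and vision events by hemodialysis, body weight or sex therefore depend on the condition in 8.2.3.4.

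**Working it through.** **The plan's own figures.** The SAP states: "The target sample size of 3400 patients with neuropathic pain is expected to have a 97% probability to detect adverse reactions occurring at the incidence". The rate it names is 0.1%, and one case or more counts as detection. Check: 1 − (1 − 0.001)^3400 = 0.967, which agrees. It also gives the lower limit of the "confidence interval for the incidence of this adverse reaction was 6.70% (incidence 7.40%, 380/5134 patients". The exact (Clopper-Pearson) lower limit for 380/5134 is 6.70%, and 3400 × 0.0670 = 227.8, which agrees with the stated 227 or more. The sample size is therefore justified by seeing individual reactions, not by the any-reaction comparison between subgroups.

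**Inputs.** From the documents: N = 3400, two-sided 5%, Fisher's exact test for a yes/no factor, outcome any adverse reaction. The documents give no any-reaction rate and no subgroup sizes, so the following are assumptions: any-reaction incidence p0 = 25% outside the group; one reaction at 0.5% outside and 4% inside the group; other reactions independent and unchanged; group size m = 68, 100 or 200.

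**Any-reaction rate inside the group.** p1 = 1 − (1 − 0.25) × (1 − 0.04)/(1 − 0.005) = 1 − 0.75 × 0.96/0.995 = 27.6%. An eightfold rise in one reaction moves the tested rate by 2.6 points.

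**Chance of significance.** This is the sum, over a ~ Bin(m, p1) and b ~ Bin(3400 − m, p0), of the probability of each pair with Fisher p < 0.05. The same sum with 4% and 0.5% gives the test on the reaction itself.

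| m | Any-reaction test (25.0% v 27.6%) | Test on the reaction (0.5% v 4%) | Expected cases inside / outside |
|---|---|---|---|
| 68 | 8% | 64% | 0.04 × 68 = 2.7 / 0.005 × 3332 = 16.7 |
| 100 | 9% | 77% | 4.0 / 0.005 × 3300 = 16.5 |
| 200 | 13% | 96% | 8.0 / 0.005 × 3200 = 16.0 |

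**Sensitivity to the assumptions.**

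- Hemodialysis group of 20 to 50, a reaction in r = 10% of them on top of a background p0 of 10% to 40%, so p1 = 1 − (1 − p0)(1 − r): the any-reaction test is significant in 7% to 49%. A test of the reaction itself (10% v 0.5%) is significant in 61% to 96%.
- Group of 100 and r = 20%: the any-reaction test is significant in 66% to 99.6%. A large effect in a larger group does get through.
- A true any-reaction rate of 35% v 25% meets the condition in about 27% (m = 34) or 45% (m = 68).
- By contrast, 29% v 25% in two halves of 1700 meets it in about 74%. The rule favours modest differences in large groups over concentrated ones in small groups.

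These figures are for a two-group Fisher test. Ordered factors such as clearance are tested for trend and were not calculated.

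**The case against.** The strongest reply is that much of the safety output does not depend on this condition. That is right. A reader might infer from 8.2.3.4 that no SOC/PT table by factor appears without significance; the tables listed above show otherwise. Prior and concomitant drug classes, target disease and initial dose have their own tables. Patients below 60 mL/min are in the renal impairment table, for all and serious reactions. Hemodialysis patients would probably be there too, assuming they are recorded as renally impaired or below 60 mL/min. SAP Section 9 also lists reactions in renal impairment and all serious reactions, so no event disappears from the report.

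What this does not supply is separation. The renal table pools everyone below 60 mL/min with everyone recorded as impaired, and a patient listing has no denominators and no comparison group. The allowance for additional analyses in 8.2.3.5 is not a commitment.

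Other tempting readings also go too far:

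- The SAP does not treat non-significance as absence of a difference. It calculates risk ratios and differences with intervals whatever the p-value, and using exploratory tests to choose follow-up tables does not contradict SAP 4.1.
- A non-monotone pattern need not fail the trend test; an asymmetric one can still be significant.
- The serious-reaction table is discretionary. Whether it is also limited to significant factors is unclear from the wording.
- The 64% to 96% belongs to a test on one reaction chosen in advance. The fix prints tables and adds no such test.

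**Conclusion.** The point holds for the factors without an unconditional SOC/PT table, chiefly hemodialysis and the clearance bands below 30 mL/min shown separately. If 8.2.3.4 is followed as written, a specific reaction concentrated in a small group is likely not to be displayed by that factor. In the main illustration the condition is missed in about 87% to 92% of surveys (100 − 13 to 100 − 8), although the excess is present in the data.

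This is a probability, not a certainty. It rests on assumed subgroup sizes and rates and on independence of the reaction from others. It also rests on the natural reading that the significance in question is on at least one adverse reaction. No primary result changes; what is at stake is whether a visible signal is laid out where a reader would look for it.

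**What to change.** In SAP 8.2.3.4, remove the significance condition for every 5.4 factor that has no unconditional SOC/PT table elsewhere, at minimum hemodialysis and each creatinine clearance category. For those factors, tabulate all adverse reactions and serious adverse reactions by SOC and PT in each subgroup, with the subgroup denominator, whatever the p-value. Replace the as-necessary wording for serious reactions accordingly, and state that p-values are descriptive only. Factors already covered need no duplicate table; a cross-reference is enough.

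The data are collected and the same table program serves. The cost is a wording change and a longer appendix, with sparse rows in the smallest groups that should be read as counts rather than as comparisons.

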8.2.3.5. Exploratory analysis

Patient demographics (see Section 8.2.2) will be tabulated and number and proportion of patients with adverse reactions will be tabulated for each SOC and PT by target disease (i.e., diagnosis of neuropathic pain).

In addition, number and proportion of patients with adverse reactions will be tabulated for each SOC and PT by subgroup based on the initial dose specified in Section 5.4.

Furthermore, additional analyses may be performed as necessary. Results from exploratory analyses will be reported only if they provide important interpretation.

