## 3 Target sample size

The target sample size is 3400 patients with neuropathic pain in total, including 3000 patients with peripheral neuropathic pain (1000 patients with post herpetic neuralgia, if possible, and 2000 patients with peripheral neuropathic pain of the types other than post herpetic neuralgia), and 400 patients with central neuropathic pain (300 patients with post-stroke pain, if possible, and other patients with pain following traumatic spinal cord injury and pain due to Parkinson's disease). For peripheral neuropathic pain, approximately 100 each of patients should be accumulated, if possible, for trigeminal neuralgia, peripheral entrapment neuropathy, iatrogenic neuropathy, neuropathy due to tumor-induced nerve compression or infiltration, posttraumatic pain, and chronic cauda equina syndrome.

[Rationale]

The target sample size of 3400 patients with neuropathic pain is expected to have a 97% probability to detect adverse reactions occurring at the incidence of 0.1% or higher in at least 1 patient. Of the adverse reactions included in the major investigation items, vision-related events are anticipated to develop at the lowest incidence during the survey. In clinical studies of the product conducted in Japan and overseas, the lower bound of the 95% confidence interval for the incidence of this adverse reaction was 6.70% (incidence 7.40%, 380/5134 patients). If this adverse reaction develops at the same incidence as in these clinical studies, this reaction is expected to occur in 227 or more of 3400 patients. Since the safety and efficacy of the product should be evaluated in patients with each type of neuropathic pain, enrollment of the following number of patients will be ensured; approximately 100 patients each, if possible, for trigeminal neuralgia, peripheral entrapment neuropathy, iatrogenic neuropathy, neuropathy due to tumor-induced nerve compression or infiltration, posttraumatic pain, and chronic cauda equina syndrome, approximately 300 patients for post-stroke pain, and a certain number of patients for pain following traumatic spinal cord injury and pain due to Parkinson's disease.

This sample size will also allow for adequate evaluation of the characteristics of other adverse reactions included in the major investigation items. The characteristics to be evaluated include time of onset and duration of adverse reactions, and these were also investigated in the clinical studies.

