Furthermore, subgroups will be defined based on initial dose (information on administration of Lyrica: dose on Day 1), and exploratory analyses will be performed in the safety analysis set and efficacy analysis set.

- Initial dose <150 mg, 150 mg, >150 mg

6. Endpoints and covariates

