8.2.4.7. Exploratory analysis

Response rate of clinical efficacy will be calculated by target disease (i.e., diagnosis of neuropathic pain) and drug class of concomitant medications for factors affecting efficacy. Analyses specified in Sections 8.2.4.2 to 8.2.4.5 will be performed by target disease for each evaluation of efficacy other than clinical efficacy. For target disease, diseases with number of patients analyzed of approx.100 or more will be examined.

Response rate of clinical efficacy will be calculated by subgroup based on the initial dose specified in Section 5.4, and patients demographics specified in Section 8.2.2 will be tabulated for ineffective patients.

Furthermore, additional analyses may be performed as necessary. Results from exploratory analyses will be reported only if they provide important interpretation.

9. Listings

The following listings will be prepared.

- Listing of patients
- Listing of patients with adverse events
- Listing of adverse reactions
- Listing of patients excluded from the safety analysis who experienced adverse reactions
- Listing of serious adverse reactions
- Listing of serious adverse events
- Listing of adverse reactions in patients with hepatic impairment
- Listing of adverse reactions in patients with renal impairment

- Listing of adverse reactions in the elderly
- Listing of adverse reactions (major investigation items)
- Listing of adverse reactions (accident-related events)
- Listing of body weight and laboratory parameters
- Listing of patient-assessed pain score
- Listing of patient-assessed sleep interference score
- Listing of patients' global impression of change (PGIC) and clinical global impression of change (CGIC)
- Listing of administration records
- Listing of initial dose and patient demographics, etc.

The following tables corresponding to appendix forms of periodical safety report will be prepared.

- Appendix Form 3 (Listing of patient summary)
- Appendix Form 2 (Summary of occurrence of adverse reactions and infections)
- Appendix Form 10 (Appendix Form 2-2) (Summary of occurrence of serious adverse events)

10. Appendices

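### SAP 8.2.3.5 and 8.2.4.7 make reporting of planned pain-type and initial-dose tables depend on whether their results are judged important

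*SAP*

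**What the plan says.** SAP 8.2.3.5 (exploratory safety analysis) plans that "number and proportion of patients with adverse reactions will be tabulated for each SOC and PT by target disease", and plans the same tabulation "by subgroup based on the initial dose specified in Section 5.4". SAP 8.2.4.7 (exploratory efficacy analysis) plans response rate by target disease and concomitant drug class. It then states that "Analyses specified in Sections 8.2.4.2 to 8.2.4.5 will be performed by target disease for each evaluation of efficacy other than clinical efficacy", and that "Response rate of clinical efficacy will be calculated by subgroup based on the initial dose specified in Section 5.4".

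Both sections close with the same two sentences. The first is "Furthermore, additional analyses may be performed as necessary". The second is "Results from exploratory analyses will be reported only if they provide important interpretation".

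SAP section 3 undertakes to perform every analysis in the plan at the final analysis. It does not speak of reporting them. Protocol section 3 explains its enrolment targets for named pain types with the words "Since the safety and efficacy of the product should be evaluated in patients with each type of neuropathic pain".

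**The concern.** Whether a result offers an important interpretation can be judged only after it has been seen. A rule of this kind for planned tables makes what appears in the report depend on what the data showed.

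The survey recruits named pain types partly so that each can be evaluated, and its results feed proper-use information and the reexamination application. If tables by pain type appear only when someone finds them important, a reader who meets a gap cannot tell an unremarkable result from an omitted one. Any differences that do appear will tend to look larger than they are.

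**Working it through.** No figure in the plan bears directly on this point. The figures in Protocol section 3 concern the whole survey, and they reproduce: 1 − (1 − 0.001)^3400 = 0.967, against the stated 97%; and 3400 × 6.70% = 227.8, against the stated 227 or more. Neither says anything about reporting by pain type. The check is therefore mainly a comparison of sections.

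**Step 1: does the rule reach planned tables?** It refers to exploratory analyses, and both sections carry that title. SAP 5.4 uses the same term for the planned work on the <150, 150 and >150 mg groups: "exploratory analyses will be performed in the safety analysis set and efficacy analysis set". Nothing in the sentence limits it to the unplanned additions.

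**Step 2: which outcome tables depend on it?**

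| Table | Planned in | Another route? |
|---|---|---|
| SOC/PT reaction proportions by target disease | 8.2.3.5 | 8.2.3.4, but only if the factor tests significant |
| Pain-score summaries and 30%/50% responders by target disease | 8.2.4.7 | Not as such; 8.2.4.6 gives adjusted pain change |
| Sleep score, PGIC, CGIC by target disease | 8.2.4.7 | Patient listings only (section 9) |
| Response rate by concomitant drug class | 8.2.4.7 | 8.2.4.6 gives concomitant medication yes/no only |
| SOC/PT reactions for <150, 150, >150 mg | 8.2.3.5 | Partial: two initial-dose by creatinine-clearance groups in 8.2.3.1 |
| Response rate for <150, 150, >150 mg | 8.2.4.7 | 8.2.4.6, in different dose bands |

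For the first row, both routes depend on the result: one on a 5% test, the other on an unstated judgement.

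**Step 3: what stands outside the rule?**
- Any-reaction incidence by every 5.4 factor, including target disease and starting daily dose (8.2.3.4).
- Clinical response rate by the same two factors, and an analysis of covariance of pain change with least squares means and 95% confidence intervals (8.2.4.6 with 8.1.1).
- Reactions in the dizziness and somnolence group by every 5.4 factor (8.2.3.1).
- PT counts, without proportions, by target disease and drug class, for diseases with about 100 or more patients (8.2.3.1).
- SOC/PT tables for two groups defined by initial dose and creatinine clearance (8.2.3.1).
- Demographics by initial dose (8.2.2).
- The listings in section 9, including reactions, pain, sleep, PGIC/CGIC and initial dose.

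The factor-by-factor tabulation in 8.2.3.1 is written for the dizziness and somnolence item only. For edema and vision events, proportions by pain type therefore rest largely on the conditional SOC/PT tables.

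**Step 4: illustration only.** Protocol section 3 gives a numeric target for eight named pain types: post herpetic neuralgia, post-stroke pain and six types at about 100 each. Assume 100 patients in each and one common true responder proportion p. The standard error is √(p(1 − p)/100): 5.0 points at p = 50%, 4.6 at 70% and 4.0 at 80%. The average highest and lowest of the eight observed proportions, from 200,000 simulated sets, are:

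| p | Highest | Lowest |
|---|---|---|
| 50% | 57.1% | 42.9% |
| 70% | 76.4% | 63.4% |
| 80% | 85.5% | 74.2% |

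So the most extreme types lie about 5.5 to 7.1 points from the truth by chance alone. With eight independent two-sided 5% tests, the chance of at least one false positive is 1 − 0.95^8 = 0.34. The 100 per type understates two targets (1000 and 300), which would vary less.

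**The case against.** The strongest reply is that the sentence directly follows the one allowing additional analyses and may be meant for those alone. The planned tables above it are stated without condition. That may well have been the intent, but the wording does not say so, and the section titles and SAP 5.4 point the other way. At best the text is ambiguous.

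It is also fair to say that an important interpretation need not mean a difference. A null result by pain type could qualify. A reader might infer that the SAP orders unremarkable results to be withheld. It does not; it permits that, with no stated criterion.

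A reader might further infer that every initial-dose result, or all pain results by pain type, could disappear, or that only any-reaction incidence and clinical response by disease are safe. The documents do not support this. Starting daily dose is an ordinary subgroup factor for safety and efficacy, pain change by target disease is covered by the analysis of covariance, and the other items in Step 3 stand as well.

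Finally, the survey is declared non-confirmatory, and much of the evaluation by pain type is planned outside the two sections. This lowers the stakes. It does not give the tables in Step 2 an unconditional place in the report.

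**Conclusion.** The point holds for the tables in Step 2 and no further. The SAP contains a rule that, as worded, allows planned tables to be reported or left out according to their results, and several of them serve a design purpose stated in the protocol. The primary analysis items, overall adverse-reaction incidence and overall response rate, are unaffected.

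No size can be attached to the resulting bias. The SAP states no threshold for reporting, so the figures in Step 4 show only how far extreme subgroups can stray by chance under the assumed inputs. They do not measure this rule. The conclusion rests on reading the sentence as it is written; under the narrower reading the defect is one of unclear wording, and the same change cures it. The change should be made, but it is not a matter on which the main results turn.

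**What to change.** In both 8.2.3.5 and 8.2.4.7, replace the closing sentence with: *All analyses specified in this section will be reported whatever their result. Any additional unplanned analyses that are performed will all be listed and labelled post hoc.*

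The cost is SAP wording and some report pages. No new data or analysis is needed. The SAP history records the survey as completed; if the SAP can no longer be amended, the same commitment can be stated and kept in the final report.
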